8.2.3. Subjects with Uremic Pruritus

All subjects with uremic pruritus meeting any of the following criteria will be excluded from this study:

1. Has a concomitant disease or a history of any medical condition that, in the opinion of the Investigator, could pose undue risk to the subject, impede completion of the study procedures, or would compromise the validity of the study measurements, including, but not limited to:
 - a. Significant systolic or diastolic heart failure (eg, New York Heart Association Class IV congestive heart failure)
2. Recent, current, or planned use of any new medications or adjustments to current medications within 14 days of Screening until the end of the study unless modification to the hemodialysis regimen is needed or for subject safety
3. Positive result for HIV or presence of actively replicating viral hepatitis due to HBV or HCV infection at Screening

4. History of malignancy of any organ system (other than localized squamous cell or basal cell carcinoma of the skin that have been excised or resolved), treated or untreated, within the past 5 years
5. Positive alcohol screen result at Screening or Day -1 or known use of drugs or tobacco at Screening
6. Significant history of abuse of drugs, solvents, or alcohol (>3 servings or units/day on average; 1 unit = 12 ounces [350 mL] of 5% alcohol beer, 5 ounces [150 mL] of 12% wine, or 1.5 ounces [45 mL] of 80 proof distilled spirits) in the past 2 years before Screening
7. Unable or unwilling to abstain from alcohol for 48 hours before Screening and from 48 hours before Day -1 until the end of the study
8. Participation in any clinical study with an investigational or approved drug/device within 30 days before Screening or is planning to participate in another clinical study while enrolled in this study (previous participation in SD-UP is allowed)
9. Allergy to any component of study drug
10. Previously participated in another dose level group in MAD-UP
11. Female who is pregnant, nursing, or intends to become pregnant during the study
12. Is directly affiliated with the study at the study site or is an immediate family member (spouse, parent, child, or sibling; biological or legally adopted) of personnel directly affiliated with the study at the study site
13. Is employed by Escient Pharmaceuticals, Inc. (that is an employee, temporary contract worker, or designee responsible for the conduct of the study) or is an immediate family member of an employee of Escient Pharmaceuticals, Inc.
14. Subject is, in the opinion of the Investigator, not suitable to participate in the study
15. Scheduled to receive a kidney transplant during the study (placement on a transplant waiting list is not exclusionary)
16. Is receiving ongoing UVB treatment or anticipates receiving such treatment during the study
17. Known noncompliance with hemodialysis treatment that, in the opinion of the Investigator, would impede completion or validity of the study
18. For subjects participating in MAD-UP, pruritus is attributed mainly to any disease unrelated to kidney disease, is only present during the hemodialysis sessions, or is attributed to a skin disorder that occurs in this population with associated itch (eg, acquired perforating dermatosis)

8.3. Study Restrictions

Unless stated otherwise, subjects must adhere to the following restrictions from Screening until the end of the study unless subject safety is compromised:

- Abstain from alcohol during the 48 hours before Screening and from 48 hours before Day -1 until the end of the study.
- Abstain from eating food containing poppy seeds for 48 hours before Screening and from 48 hours before Day -1 until the end of the study.
- Avoid strenuous exercise from the 72 hours before Screening until the end of the study.
- Do not take any new prescribed medication, over-the-counter (OTC) medication, vitamin preparations or other food supplements, health supplements, or herbal remedies during the study (unless done so in consultation with the Medical Monitor).
 - An exception is made for acetaminophen (up to 1 gram per 24-hour period) as permitted by the Investigator for the treatment of headache or any other pain. Other medication to treat AEs may only be prescribed if deemed necessary by the Investigator.
- Maintain current dose and regimen of all prescribed medication, OTC medication, vitamin preparations or other food supplements, health supplements, and herbal remedies during the study (unless changed in consultation with the Medical Monitor).
- For subjects with cholestatic or uremic pruritus, do not undergo UVB treatment
- Do not use any drugs of abuse.
- Do not use any investigational drugs/devices.
- Do not donate blood or plasma.

8.4. Subject Withdrawal Criteria

Subjects will be free to withdraw consent and discontinue participation from the study at any time and without prejudice to further care per standard clinical practice. A subject's participation in the study may also be discontinued at any time at the discretion of the Investigator or Sponsor. Individual subjects may be excluded from the study if a medical records review indicates protocol deviations, or if other factors suggest that the subject will not be a suitable study subject.

If a subject is withdrawn from the study, the reason will be recorded on the electronic case report form (eCRF) page and the Sponsor will be notified promptly.

Subjects who terminate the treatment period early should complete the early study termination evaluations as soon as possible after the last dose of study drug, ideally within 2 days after the last dose. If termination occurs during the treatment period, the subject will have a follow-up visit approximately 1 week (± 1 day) after the last dose of study drug. If termination of the treatment period occurs while participating in a MAD segment, the subject will also have a follow-up visit approximately 2 weeks (± 2 days) after the last dose of study drug. After the final

study visit, further standard of care treatment will be determined by the subject and treating physician. Subjects who discontinue before completing the treatment period or are non-evaluable may be replaced in order to meet evaluable subject requirements.

9. TREATMENT OF SUBJECTS

9.1. Treatment Assignment

Treatment assignments for healthy subjects, subjects with cholestatic pruritus, and subjects with uremic pruritus are described in Sections 7.1.1, 7.1.2, and 7.1.3, respectively.

The Sponsor will allocate sequential randomization codes and kit numbers for each dose level from the randomization code and kit assignment list. Sites will request the allocated randomization and kit numbers from the Sponsor in advance of dosing by contacting [REDACTED].

9.2. Treatment Compliance

To ensure treatment compliance, the Investigator or authorized designee will administer all doses of study drug. Compliance will be further confirmed by bioanalytical assessment of EP547 in plasma.

The exact times of study drug administration and the number of capsules administered will be recorded in the eCRF.

9.3. Randomization and Blinding

9.3.1. Randomization

Subjects will be assigned a subject number after signing the Informed Consent Form (ICF). Subjects who meet all eligibility criteria will be randomized and assigned a randomization number just before dosing. Subjects in SAD-HS, MAD-HS, MAD-CP, and MAD-UP will be assigned to EP547 or placebo in a 3:1 ratio (EP547:placebo), with a block size of 4 for the MAD segments. The randomization code for each dose level will be generated by the CRO and managed by the Sponsor. Subjects in SD-CP and SD-UP will only receive EP547 and do not require randomization.

Subjects who withdraw for any reason without completing all screening evaluations successfully will be considered “screening failures”.

9.3.2. Blinding

Although SAD-HS and all of the MAD segments will be conducted in a blinded manner (ie, subjects, Investigator, study-site personnel, and CRO staff not involved in PK sample analysis or regulatory reporting will be blinded to treatment), the Sponsor, including the Sponsor Medical Monitor, will be unblinded to treatment assignment to assess safety on an ongoing basis.

Communication between the blinded Investigator and unblinded Sponsor will be managed to ensure treatment assignment is not revealed. The SD-CP and SD-UP segments are not placebo-controlled (ie, all subjects will receive EP547) and will be conducted in an unblinded manner.

9.3.2.1. Emergency Unblinding

Blinding codes should only be broken in emergency situations for reasons of subject safety and when knowledge of the treatment assignment will impact the clinical management of the subject.

Every reasonable attempt should be made to complete the post-treatment evaluation procedures before unblinding as knowledge of the study drug could influence subject assessment.

If unblinding is required at the study site, code break envelope(s) will be available for all subjects. The sealed envelope(s) containing the treatment assignment(s) will be kept in a location that is locked with restricted access. The Investigator must contact the Sponsor and Medical Monitor to discuss the decision to unblind a subject's treatment. After approval from the Sponsor or Medical Monitor, or if attempts to reach the Sponsor and Medical Monitor are unsuccessful and immediate knowledge of the treatment assignment will impact the clinical management of the subject, the Investigator will be allowed to break the code to know whether a subject received EP547 or placebo. If opened, the name of the person who opened it, the date and time of opening, and the reason for opening must be written on the envelope. The Sponsor will be informed in case of unblinding at the earliest appropriate time.

9.3.2.2. Unblinding for Regulatory Reporting

Access to individual treatment assignments will be made available to the appropriate individual(s) at the CRO responsible for unblinding suspected unexpected serious adverse reactions for reporting to the Regulatory Authorities.

9.4. Study Visits

Subjects should fast for at least 8 hours before study days that require a blood sample for assessment of clinical chemistry, multiple blood samples for PK, [REDACTED]. Water is acceptable in the morning of site visits and each study day while confined to the study site to ensure the subject is hydrated for laboratory sample collection. On days with multiple blood samples for PK, study drug will be administered with approximately 240 mL of water, additional water will not be allowed from 1 hour predose to 1 hour postdose, and subjects will remain fasted until after the 4-hour PK blood sample is collected. If a subject with ESRD has a daily fluid restriction, study drug may be administered with a smaller volume of water at the Investigator's discretion.

[REDACTED]

Study procedures are listed for each visit in the following sections and summarized in the Schedule of Assessments ([Appendix A](#) for the single dose segments and [Appendix B](#) for the multiple dose segments). Further details regarding safety, PK, cardiodynamic, and PD assessments are located in Sections [11](#), [12](#), [13](#), and [14](#), respectively.

9.4.1. SAD Segments

9.4.1.1. Screening Period

9.4.1.1.1. Visit 1 (Day -28 to Day -2)

During the screening period, subjects are to arrive at the clinic after an overnight fast (at least 8 hours) and will undergo assessments at the site to determine their study eligibility. Subjects will be screened and should meet all inclusion criteria and none of the exclusion criteria to be

enrolled in the study. Any questions regarding eligibility may be discussed with the Medical Monitor.

The following assessments may be conducted over more than 1 day but must be completed between Day -28 and Day -2:

- Completion of informed consent before performance of any study procedures or assessments
- Medical history
- Height
- Complete physical examination
- Vital signs
- Standard 12-lead ECG
- Body weight
- Laboratory assessments:
 - HIV, HBV, and HCV serology
 - Drug and cotinine screens (SAD-HS and SD-CP only)
 - Alcohol screen
 - Serum pregnancy test (females only)
 - Follicle-stimulating hormone (FSH) (females only)
 - Chemistry and hematology
 - Urinalysis (SAD-HS and SD-CP only)
 - Coagulation
- Assessment of baseline concomitant medications, including:
 - All medications taken within 14 days before Screening
 - Medications taken to treat a cholestatic disorder or ESRD within 12 weeks before Screening (SD-CP and SD-UP only)
 - Medications known to impact pruritus within 4 weeks before Screening (SD-CP and SD-UP only)
- Assessment of AEs
- Eligibility check

Screening results will be reviewed by the Investigator to determine the subject's eligibility. Subjects who are confirmed to be eligible will be asked to return to the site for Visit 2 (Day -1) to enroll in the study.

9.4.1.1.2. Visit 2 (Day -1) - Admission

Subjects who meet all eligibility requirements will be admitted for mandatory confinement at the clinic during Visit 2 (Day -1) and will undergo the following assessments:

- [REDACTED]
- [REDACTED]
- Abbreviated physical examination
- Laboratory assessments:
 - Drug and cotinine screens (SAD-HS and SD-CP only)
 - Alcohol screen
 - Urine pregnancy test (SAD-HS and SD-CP females only)
- Assessment of concomitant medication usage
- Assessment of AEs
- Hemodialysis (SD-UP only)
- Eligibility check

Visit 2 (Day -1) results will be reviewed by the Investigator to confirm the subject's eligibility. Subjects who are confirmed to be eligible will continue to remain confined to the clinic until completion of Visit 2 (Day 3).

9.4.1.2. Treatment Period

9.4.1.2.1. Visit 2 (Day 1) - Predose

For subjects in SD-UP, Day 1 must be the day after a hemodialysis session. Subjects will continue to be confined at the clinic during Visit 2 (Day 1) and will undergo the following assessments before administration of study drug:

- Vital signs
- Standard 12-lead ECG
- Body weight
- Laboratory assessments:
 - Chemistry and hematology
 - Urinalysis (SAD-HS and SD-CP only)
 - [REDACTED]
- Assessment of concomitant medication usage
- Assessment of AEs
- Blood sample draw for PK assessment

- Continuous digital 12-lead ECG recording for Holter monitoring beginning approximately 1 hour before study drug administration (SAD-HS only)
- Urine collection for PK assessment from -6 to 0 hours predose (SAD-HS only)
- Allocation to EP547 or placebo in a 3:1 ratio (SAD-HS only)

Upon completion of the assessments listed above, study drug is to be administered orally as intact capsules (swallowed whole, not chewed or crushed), and taken with water. All dose levels in SAD-HS will be dosed according to a sentinel dosing design (Section 7.1.1). All subjects in SD-CP and SD-UP will receive EP547.

9.4.1.2.2. Visit 2 (Day 1) - Postdose

Subjects will continue to be confined at the clinic during Visit 2 (Day 1) and will undergo the following assessments after administration of study drug:

- Assessment of concomitant medication usage
- Assessment of AEs
- Urine collection for PK assessment from >0 to 6, >6 to 12, and >12 to 18 hours postdose (SAD-HS only)
- Blood sample draw for PK assessment at 0.25, 0.5, 1, 1.5, 2, 2.5, 3, 4, 6, 9, and 12 hours postdose
- Continue 24-hour continuous digital 12-lead ECG recording for Holter monitoring (SAD-HS only)
- Vital signs at 1, 2, 4, 9, and 12 hours postdose
- Standard 12-lead ECG at 3 hours postdose

9.4.1.2.3. Visit 2 (Day 2)

Subjects will continue to be confined at the clinic during Visit 2 (Day 2) and will undergo the following assessments:

- Laboratory assessments:
 - Chemistry and hematology
 - Urinalysis (SAD-HS and SD-CP only)
- Assessment of concomitant medication usage
- Assessment of AEs
- Blood sample draw for PK assessment at 18, 24, and 36 hours postdose
- End 24-hour continuous digital 12-lead ECG recording for Holter monitoring (SAD-HS only)
- Urine collection for PK assessment from >18 to 24, >24 to 30, and >30 to 36 hours postdose (SAD-HS only)

- Vital signs at 24 hours postdose

9.4.1.2.4. Visit 2 (Day 3) - Discharge

Subjects will continue to be confined at the clinic during Visit 2 (Day 3) until completion of the following assessments:

- Laboratory assessments:
 - Chemistry and hematology
 - Urinalysis (SAD-HS and SD-CP only)
- Assessment of concomitant medication usage
- Assessment of AEs
- Vital signs at 48 hours postdose
- Standard 12-lead ECG at 48 hours postdose
- Urine collection for PK assessment from >36 to 42 and >42 to 48 hours postdose (SAD-HS only)
- Blood sample draw for PK assessment at 48 hours postdose

Subjects may be discharged from the clinic after completion of all assessments listed above.

9.4.1.3. Safety Follow-Up Visit (Visit 3 [Day 8])

Subjects are to arrive at the clinic after an overnight fast (at least 8 hours) and will undergo the following assessments during the ± 1 -day visit window for Visit 3 (Day 8):

- Complete physical examination
- Vital signs
- Body weight
- Laboratory assessments:
 - Serum pregnancy test (females only)
 - Chemistry and hematology
 - Urinalysis (SAD-HS and SD-CP only)
- Assessment of concomitant medication usage
- Assessment of AEs
- Blood sample draw for PK assessment

9.4.1.4. Early Study Termination Visit

Subjects who discontinue from the study early should have the Early Study Termination Visit conducted as soon as possible after the dose of study drug, ideally within 2 days after the dose of

study drug. Subjects are to arrive at the clinic after an overnight fast (at least 8 hours) and will undergo the following assessments during the Early Study Termination Visit:

- Complete physical examination
- Vital signs
- Standard 12-lead ECG
- Body weight
- Laboratory assessments:
 - Serum pregnancy test (females only)
 - Chemistry and hematology
 - Urinalysis (SAD-HS and SD-CP only)
- Assessment of concomitant medication usage
- Assessment of AEs

9.4.2. MAD Segments

9.4.2.1. Screening Period

9.4.2.1.1. Visit 1 (Day -28 to Day -4)

During the screening period, subjects are to arrive at the clinic after an overnight fast (at least 8 hours) and will undergo assessments at the site to determine their study eligibility. Subjects will be screened and should meet all inclusion criteria and none of the exclusion criteria to be enrolled in the study. Any questions regarding eligibility may be discussed with the Medical Monitor.

The following assessments may be conducted over more than 1 day but must be completed between Day -28 and Day -4, unless specified otherwise:

- Completion of informed consent before performance of any study procedures or assessments
- Medical history
- Height
- Complete physical examination
- Vital signs
- Standard 12-lead ECG
- Body weight
- Laboratory assessments:
 - HIV, HBV, and HCV serology
 - Drug and cotinine screens (MAD-HS and MAD-CP only)

- Alcohol screen
- Serum pregnancy test (females only)
- FSH (females only)
- Chemistry and hematology
- Urinalysis (MAD-HS and MAD-CP only)
- Coagulation
- [REDACTED]
- Assessment of baseline concomitant medications, including:
 - All medications taken within 14 days before Screening
 - Medications taken to treat a cholestatic disorder or ESRD within 12 weeks before Screening (MAD-CP and MAD-UP only)
 - Medications known to impact pruritus within 4 weeks before Screening (MAD-CP and MAD-UP only)
- Assessment of AEs
- [REDACTED]
- [REDACTED]
- [REDACTED]
- [REDACTED]
- [REDACTED]
- [REDACTED]
- Eligibility check

Screening results will be reviewed by the Investigator to determine the subject's eligibility. Subjects who are confirmed to be eligible will be asked to return to the site for Visit 2 (Day -1) to enroll in the study.

9.4.2.1.2. Visit 2 (Day -1) – Admission

Subjects who meet all eligibility requirements will be admitted for confinement at the clinic during Visit 2 (Day -1) and will undergo the following assessments:

- [REDACTED]
- [REDACTED]
- [REDACTED]
- Abbreviated physical examination

- Laboratory assessments:
 - Drug and cotinine screens (MAD-HS and MAD-CP only)
 - Alcohol screen
 - Urine pregnancy test (MAD-HS and MAD-CP females only)
- Assessment of concomitant medication usage
- Assessment of AEs
- █ [REDACTED]
- █ [REDACTED]
- Eligibility check

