8.1.3. Subjects with Uremic Pruritus

To be eligible for study participation, all subjects with uremic pruritus must meet all the following inclusion criteria:

1. Age 18 to 80 years, inclusive
2. Has ESRD and is receiving hemodialysis 3× per week of at least 4 hours in duration for ≥3 months before Screening; hemodialysis must be adequate (ie, ≥2 urea reduction ratio measurements ≥65% on different hemodialysis days from the month before Screening to Day -1)
3. If female, must be willing to not donate eggs from the time of informed consent until 30 days after the last dose of study drug and:
 - a. Is surgically sterile; or
 - b. Has been amenorrhoeic for ≥1 year and is over the age of 55 years; or
 - c. Has a negative serum pregnancy test at Screening and agrees to use a barrier method (eg, condom) during intercourse and at least 1 other acceptable contraceptive measure (eg, hormonal contraceptives, intrauterine device, vasectomized partner, or abstinence) from the time of informed consent until 30 days after the last dose of study drug

Abstinence is considered a highly effective method of birth control if the subject refrains from heterosexual intercourse from the time of informed consent until 30 days after the last dose of study drug. The reliability of sexual abstinence needs to be evaluated in relation to the duration of the study and the preferred and usual lifestyle of the subject.
4. If male and is not surgically sterile for at least 3 months, must be willing to not donate sperm and must agree to use a barrier method of contraception (eg, condom) during intercourse and at least 1 other acceptable contraceptive measure (eg, hormonal contraceptives, intrauterine device, female surgical sterilization, male vasectomy, or abstinence) from Screening through 90 days after the last dose of study drug
5. No clinically relevant medical history, physical examination, vital sign, standard 12-lead ECG, chemistry, hematology, or coagulation results at Screening beyond what is

expected for subjects with ESRD that would place the subject at undue risk as deemed by the Investigator

6. Must be able to communicate well with the Investigator, understand and comply with the requirements of the study (including required confinement periods), and understand and provide written consent
7. For subjects participating in MAD-UP, has experienced self-reported daily or near-daily moderate to severe pruritus for >4 weeks before Screening
8. [REDACTED]

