APPENDIX A. SCHEDULE OF ASSESSMENTS FOR THE SINGLE DOSE SEGMENTS

Visit	Screening ^a		Treatment Period				Safety Follow-Up	Early Study Term ^b	Notes
	Visit 1	Visit 2				Visit 3			
Study Day (Visit Window)	-28 to -2	-1	1 (pre-dose)	1 (post-dose)	2	3	8 (±1)		
Mandatory Confinement		X	X	X	X	X			
Admission		X							
Discharge						X			
General Assessments									
Informed consent	X								
Medical history	X								
Height	X								Measured using a stadiometer with no shoes.
FSH (females only)	X								
HIV, HBV, HCV serology	X								
Drug and cotinine screens (SAD-HS and SD-CP only)	X	X							Day -1 will be conducted locally.
Alcohol screen	X	X							Will be conducted locally.
Eligibility check	X	X							
Randomization			X						All dose levels in SAD-HS will be dosed according to a sentinel dosing design (Section 7.1.1). All subjects in SD-CP and SD-UP will receive EP547.
Study drug administration			X						Administered orally as intact capsules with water. For SD-UP, Day 1 (study drug administration) must be the day after a hemodialysis session.
Hemodialysis (SD-UP only)		X							Refer to note above.
Safety Assessments									
Pregnancy testing	X	X					X	X	Urine pregnancy test on Day -1 for all female SAD-HS and SD-CP subjects and serum pregnancy test for all female subjects for Screening, Day 8, and Early Study Term, if applicable.

Visit	Screening ^a		Treatment Period				Safety Follow-Up	Early Study Term ^b	Notes
	Visit 1	Visit 2	Visit 3						
Study Day (Visit Window)	-28 to -2	-1	1 (pre-dose)	1 (post-dose)	2	3	8 (±1)		
Physical examination	C	A					C	C	Will be either complete (C) or abbreviated (A) (Section 11.7).
Standard 12-lead ECG	X		X	X		X		X	To be performed in a supine position after ≥5 min of rest during Screening; predose and at 3 h postdose on Day 1; 48 h postdose on Day 3; and Early Study Term, if applicable.
Vital signs	X		X	X	X	X	X	X	Includes supine systolic and diastolic blood pressure, pulse rate, oxygen saturation, body temperature, and respiratory rate, measured after ≥5 min of rest at Screening; predose and at 1, 2, 4, 9, and 12 h postdose on Day 1; 24 h postdose on Day 2; 48 h postdose on Day 3; on Day 8; and Early Study Term, if applicable.
Body weight	X		X				X	X	Should be measured with no shoes on and using a calibrated scale throughout the study.

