APPENDIX B. SCHEDULE OF ASSESSMENTS FOR THE MULTIPLE DOSE SEGMENTS

Visit		Screening ^a		Treatment Period									Safety Follow-Up ^b		Early Study Term ^c	Notes
		Visit 1		Visit 2									Visit 3	Visit 4		
Study Day (Visit Window)		-28 to -4	-1	1 (pre-dose)	1 (post-dose)	2	3	4	5	6	7	8	14 (±1)	21 (±2)		
MAD-HS	Mandatory Confinement		X	X	X	X	X	X	X	X	X	X				
	Admission		X													
	Discharge											X				
MAD-CP	Mandatory Confinement		X	X	X	X					X	X				For Days 3-6, subjects may choose to remain confined, return to the site each morning, or have a nurse visit their home to the complete scheduled assessments.
	Admission		X							X						
	Discharge					X					X					
MAD-UP	Mandatory Confinement		X	X	X	X				X	X	X				For Days 3-5, subjects may choose to remain confined, return to the site each morning, or have a nurse visit their home to the complete scheduled assessments.
	Admission		X							X						
	Discharge					X					X					
General Assessments																
Informed consent		X														
Medical history		X														
Height		X														Measured using a stadiometer with no shoes.
FSH (females only)		X														
HIV, HBV, HCV serology		X														
Drug and cotinine screens (MAD-HS and MAD-CP only)		X	X													Day -1 will be conducted locally.

Visit	Screening ^a		Treatment Period										Safety Follow-Up ^b		Early Study Term ^c	Notes
	Visit 1	Visit 2	1 (pre-dose)	1 (post-dose)	2	3	4	5	6	7	8	14 (±1)	21 (±2)			
Study Day (Visit Window)	-28 to -4	-1	1 (pre-dose)	1 (post-dose)	2	3	4	5	6	7	8	14 (±1)	21 (±2)			
Alcohol screen	X	X														Will be conducted locally.
Eligibility check	X	X														
Randomization			X													Subjects in each dosing group will be randomized in a 3:1 ratio (EP547:placebo).
Study drug administration			X		X	X	X	X	X	X	X					Administer study drug QD for 7 days as intact capsules with water. For MAD-UP, administer study drug 4 to 6 h before the hemodialysis session on Days 1, 4, and 6 and at approximately the same time of day on Days 2, 3, 5, and 7 (days without a hemodialysis session).
Hemodialysis (MAD-UP only)				X			X		X							Refer to note above.
Safety Assessments																
Pregnancy testing	X	X										X	X	X		Urine pregnancy test on Day -1 for all female MAD-HS and MAD-CP subjects and serum pregnancy test for all female subjects for Screening, Days 14 and 21, and Early Study Term, if applicable.

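### Women in SD-UP and MAD-UP are the only women with no pregnancy test at admission or before dosing on Day 1; their last scheduled test can be 28 days old, against 1 day elsewhere

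*Protocol*

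**What the plan says.** All women have a serum pregnancy test at Screening. For the multiple dose segments, Protocol 9.4.2.1.1 lists "Serum pregnancy test (females only") among assessments that "must be completed between Day -28 and Day -4, unless specified otherwise". Section 9.4.1.1.1 has the same test for the single dose segments, with a window that closes at Day -2.

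A second test follows on Day -1, but not for everyone. Section 9.4.1.1.2 lists "Urine pregnancy test (SAD-HS and SD-CP females only") and section 9.4.2.1.2 lists "Urine pregnancy test (MAD-HS and MAD-CP females only"). Section 11.9 names the same four segments for the urine test. The food effect addendum (9.2.1.2 and its Appendix A) also has a Day -1 urine test for all women.

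The schedule notes give the serum timepoints. Appendix A has "serum pregnancy test for all female subjects for Screening, Day 8, and Early Study Term, if applicable". Appendix B has "serum pregnancy test for all female subjects for Screening, Days 14 and 21, and Early Study Term, if applicable". Neither note includes Day -1 or Day 1.

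For women with uremic pruritus who qualify through contraception, criterion 3c in 8.1.3 reads "Has a negative serum pregnancy test at Screening and agrees to use a barrier method" and goes on to require a second contraceptive measure, from consent onwards. Exclusion criterion 11 in 8.2.3 bars pregnant women, and 11.2.3 requires study drug to stop at once if a subject becomes pregnant.

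**The concern.** The Amendment 1.0 summary in Appendix I explains the change: urine-based assessments were dropped for subjects with end-stage renal disease because they may pass little or no urine. That is a reason to change the specimen. It does not explain why the check itself should lapse, because the same women give serum for every other pregnancy test in the protocol, and blood is drawn from them before dosing on Day 1 for chemistry, hematology and PK (9.4.1.2.1 and 9.4.2.2.1).

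The same amendment also removed the drug and cotinine screens for these subjects. There the sponsor did compensate, by rewriting exclusion criterion 5 to cover known drug or tobacco use at Screening. No matching change was made for pregnancy, and the documents give no reason for the difference.

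At stake is a pregnancy that begins after Screening. In the healthy and cholestatic segments the Day -1 test is there to catch it before a first-in-human drug is given. In SD-UP and MAD-UP the Day -1 eligibility check has no current result to work from, so exclusion criterion 11 cannot be confirmed by a test at that point.

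**Working it through.** The plan states no figure for this interval, so there is none to reproduce. The check is date arithmetic on the visit windows.

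**Inputs**
- Screening window: Day -28 to Day -2 in the single dose segments (9.4.1.1.1), Day -28 to Day -4 in the multiple dose segments (9.4.2.1.1).
- Day -1 test: present in SAD-HS, SD-CP, MAD-HS, MAD-CP and FE-HS, absent in SD-UP and MAD-UP.
- Next scheduled test after dosing: Day 8 in the single dose segments and Day 14 in the multiple dose segments, each ±1 day (Appendices A and B).
- Day numbering: first dose is Day 1 and there is no Day 0 (SAP 3.2).

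**Formulas**
- Age of a Day -k test at first dose = k days.
- Days from first dose to Day n = n - 1.
- Longest gap between scheduled tests = k + (n - 1), plus 1 if the follow-up visit falls at the end of its window.

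**Results**

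| Segment | Last scheduled test before dosing | Age at first dose | Longest gap to next scheduled test | With +1-day window |
|---|---|---|---|---|
| SD-UP | Screening serum, Day -28 to -2 | 2 to 28 days | 28 + 7 = 35 days | 36 days |
| MAD-UP | Screening serum, Day -28 to -4 | 4 to 28 days | 28 + 13 = 41 days | 42 days |
| SAD-HS, SD-CP | Day -1 urine | 1 day | 1 + 7 = 8 days | 9 days |
| MAD-HS, MAD-CP | Day -1 urine | 1 day | 1 + 13 = 14 days | 15 days |

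In FE-HS the test is also 1 day old at dosing, in both periods. The MAD-UP gap spans all 7 doses. An early termination visit would shorten the gap, because it carries a serum test (9.4.1.4 and 9.4.2.4).

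**Could the test be hidden by redaction?** The visit lists contain blacked-out lines. The pregnancy-testing rows and notes in Appendices A and B are intact, however, and they set out the serum timepoints.

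**The case against.** Several points on the other side deserve weight.

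- **Section 11.9 is ambiguous.** After limiting the Day -1 urine test to four segments, it sends all remaining pregnancy testing to serum. The pregnancy rows in both appendices mark Day -1 without a segment limit in the row label, unlike the urinalysis and drug screen rows. A site could read the two together as a Day -1 serum test for women with uremic pruritus. The appendix notes do not support that reading, because they name the serum visits and Day -1 is not among them. What stands is that the wording needs to be made clear.
- **Contraception is required from consent**, so it covers the screening interval. This lowers the risk. But the rule is the same for healthy and cholestatic women, and the protocol still tests them on Day -1.
- **The omission is consistent and deliberate.** The visit lists, 11.9 and both appendices agree, and the amendment records the change. That shows the urine test was meant to go. It does not give a reason for leaving the check unreplaced.
- **Few women may be affected.** Women who are surgically sterile, or over 55 and amenorrhoeic for at least a year, qualify without the test. This stands.

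A reader might also infer that these women are dosed with no pre-dose pregnancy test at all. The documents contradict that, since every woman has the Screening serum test. Nor is the exclusion wholly unenforceable: a known or reported pregnancy can still be acted on at the Day -1 eligibility check. What is missing is confirmation by a current test.

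**Conclusion.** The gap is real and specific to one population. Women in SD-UP and MAD-UP have no pregnancy test at admission or before dosing on Day 1, and scheduled testing would not detect before dosing a pregnancy that began after Screening.

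The size needs careful statement:
- Twenty-eight days is the maximum that the windows allow, not a typical interval. The documents give no distribution of screening dates.
- The number of women of childbearing potential is not given. The upper limit of 30 subjects with uremic pruritus in 7.2 covers both sexes and ages 18 to 80, so it should not be read as the number affected.
- Exposure to EP547 would not follow in every case. MAD-UP is randomized 3:1, so one subject in four receives placebo. All SD-UP subjects receive EP547.
- Detection is not confined to the follow-up visits, because early termination also has a serum test.

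No endpoint or analysis is affected. This is a cheap improvement to subject protection and to consistency across segments.

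**What to change.** Reconcile the uremic pruritus schedule with the other segments. Add a serum pregnancy test for SD-UP and MAD-UP women on Day -1, with the result available before the Day 1 dose so that it can inform the eligibility check already scheduled. The text to amend is 9.4.1.1.2, 9.4.2.1.2, 11.9 and the pregnancy-testing notes in Appendices A and B. In 11.9, state which visits the general serum clause covers and where the Day -1 serum test is run. If the sponsor prefers to keep the difference, the protocol should give the reason.

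The cost is one extra blood tube per woman at an existing visit, plus an amendment. There is also a logistical cost: under 11.9 only the urine pregnancy test is run locally and all other planned safety tests go to the central laboratory, so sites enrolling these subjects need a local or rapid-turnaround serum assay.
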